3.4.4.3. Missing Data Handling

For change in SES-CD at Week 12, missing data will be assumed MCAR there will be no imputation of missing data.

For binary endpoints missing data will be imputed with non-responder imputation with the exception of data missing due to COVID-19, in these instances the data will be assumed missing completely at random and not analyzed.

3.4.5. Sensitivity Analyses

No sensitivity analysis will be performed for secondary endpoints.

3.4.6. Supplementary Analyses

All subgroup analyses outlined in section 3.3.6.3 will be performed on the secondary endpoints. Descriptive summaries of change in each SES-CD segment at Week 12 will also be presented.

3.5. Multiplicity Adjustment

There will be no hypothesis testing of secondary endpoints. Adjustment of multiplicity on the primary endpoint is outlined in Section 3.3.3.

3.6. Exploratory Endpoint(s) Analyses

3.6.1. Exploratory Endpoint(s)

[Redacted text block containing multiple paragraphs of exploratory endpoint analyses, all content obscured by black bars.]

- █ [REDACTED]
- █ [REDACTED]
- █ [REDACTED]
- █ [REDACTED]
- █ [REDACTED]
- █ [REDACTED]
- █ [REDACTED]

3.6.2. Definition of Exploratory Endpoint(s)

[REDACTED]

█ [REDACTED]

[REDACTED]

- █ [REDACTED]
- █ [REDACTED]

█ [REDACTED]

[REDACTED]

[REDACTED]

█ [REDACTED]

[REDACTED]

[REDACTED]

[REDACTED]

█ [REDACTED]

[REDACTED]

[REDACTED]

[REDACTED]

█ [REDACTED]

[REDACTED]

[REDACTED]

[REDACTED]

█ [REDACTED]

[REDACTED]

[REDACTED]

[REDACTED]

[Redacted text block]

3.6.3. Exploratory Efficacy Analyses

[Redacted text block]

- | [Redacted list item]
- | [Redacted list item]
- | [Redacted list item]

[Redacted text block]

[Redacted text block]

3.6.4. Supplementary Analyses

3.6.4.1. Subgroup analysis

To characterize the consistency of the treatment effect for endoscopic remission each of the subgroups in Section 3.3.6.3 will be performed.

3.7. Safety Analyses

The analysis of safety and tolerability data includes an overall summary of tolerability, adverse event preferred terms by body/organ system, drug exposure (duration of treatment), dosing information/compliance clinical laboratory results, vital signs and ECGs. Tables summarizing the adverse events reported by subjects who died, experienced non-fatal serious adverse events (SAE), or prematurely discontinued the study due to adverse event (AEs) will be prepared.

In general, inferential statistical tests are not performed for adverse event incidence rates.

For all safety analyses, the safety analysis population will be used.

For summaries on exposure, compliance and adverse events for the study overall (Induction and ATE),

3.7.1. Extent of Exposure

Study drug exposure will be summarized using the 8-point descriptive summary presenting number of doses and duration of treatment separately for the induction phase and complete study separately.

Duration of treatment will be displayed in weeks and calculated for the induction period as:

$$\frac{(last\ induction\ phase\ dose\ date - first\ dose\ date + 1)}{7}$$

*Last induction phase dose date is considered to be the Week 12 visit dose administration date for those that reach the Week 12 visit or equal to date of last study drug return for those who discontinue prior to Week 12 visit.

Duration of treatment for the entire study period will also be displayed in weeks and calculated as:

$$\frac{(last\ study\ drug\ return\ date - first\ dose\ date + 1)}{7}$$

Calculated values will be rounded to 1 significant digit in the analysis datasets and summary statistics will be presented to the follow significant digits:

- Mean, median, Q1, Q3: 1 significant digit
- Standard deviation: 2 significant digits
- Minimum, maximum: 1 significant digit

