6.3.15. Early Study Drug Discontinuation

Subjects who prematurely discontinue the study drug due to adverse events (AEs), lack of response, or any other reason besides withdrawal of consent during Induction or ATE will be asked to return for an Early Study Drug Discontinuation visit. This visit will be conducted within 5 days after the last dose of study drug, if possible. Subjects will also return for the EOS visit for collection of safety data and assessment of disease activity.

During ATE, subjects should be assessed for clinical benefit and if there is no clinical benefit, as deemed by the investigator, the subject should stop study drug treatment and be withdrawn from the study.

Subjects should be instructed to fast from food and non-clear fluids on the evening prior to the Early Study Drug Discontinuation visit to ensure a minimum 8-hour fast prior to the fasted blood sample collection.

The following procedures will be performed at the Early Study Drug Discontinuation visit:

- Tobacco use status
- Vital signs
 - Heart rate (HR) and systolic and diastolic blood pressure (BP)
 - Respiratory rate
 - Body Temperature
- 12-lead ECG
- Physical examination to be conducted according to local practice
- Fistula drainage assessment (if applicable) to determine the number of fistula and confirm draining is occurring.
- Weight
- Blood collection
 - Hematology
 - Serum chemistry
 - Overnight fasting lipid panel
 - [REDACTED]

- [REDACTED]
- Urine collection
 - Urinalysis
 - Pregnancy test for females of childbearing potential – If urine b-hCG test is positive, confirmation with serum b-hCG test is required
 - Fecal collection [may be collected within 3 full days (approximately 72 hours) prior to the visit; however, it is preferable that the stool sample be collected during the first bowel movement in the morning]
 - [REDACTED]
 - Disease Assessments
 - CDAI Components
 - Abdominal Pain and Total Stool Frequency Scores
 - [REDACTED]
 - [REDACTED]
 - Perform drug accountability and review subject's compliance with study drug dosing
 - Review concomitant medications
 - Adverse event assessment (AEs, SAEs, Adverse Events of Special Interest)
 - Review diary completion and compliance; counsel subject as needed Description of Study Assessments

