- I. Study drug administration will be in clinic on Day 1, Week 4, Week 8, Week 12, ATE Day 1, ATE Week 4, ATE Week 8, ATE Week 16, ATE Week 24, ATE Week 36, and ATE Week 48 on an empty stomach from the night before after all pre-dose assessments (with the exception of [REDACTED], which may be done post-visit on the same day) and procedures have been completed. Subject will take the study drug at home for the rest of the study. The last dose of Induction study drug will be taken at the Week 12 clinic visit. No new study drug will be dispensed between the Week 12 clinic visit and ATE Day 1.
- J. Subjects will be provided with an electronic diary (or paper diary if electronic diary is not available) at the Screening Stage 1 visit and instructed on daily diary completion, including symptom monitoring and study drug dosing details. Diaries of symptoms will be collected daily from the Screening Stage 1 visit through the EOS visit. Study drug dosing details will be entered from Day 1 (Induction) through ATE Week 48 (or the last dose of study drug, if the subject prematurely withdraws from study drug). Diary completion will be monitored for completeness at each return study visit after the electronic diary is dispensed (i.e., Screening Stage 2 through the EOS visit). Subjects will be counseled on missed study drug doses and missed diary entries.
- K. Corticosteroid taper, for those that are on corticosteroid at Screening Stage 1, should be initiated at the Week 8 visit.
- L. Site personnel to call subjects approximately 2 weeks prior to Week 12 visit for reminder of compliance of diary completion. The site will also review compliance on corticosteroid taper (as applicable), review upcoming schedule for Week 12 and the reminders in preparation for the visit.
- M. AE assessments are to include collection and reporting of AEs, SAEs, and AEs of Special Interest (AESIs).
- N. Urine beta human chorionic gonadotropin (b-hCG) testing will be performed before dosing when dosing in-clinic and anytime during all other visits for females of childbearing potential to confirm absence of pregnancy. If urine b-hCG test is positive, confirm with serum b-hCG test.
- O. Required for postmenopausal females.

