3.2.1. Subject Disposition and Completion Status

The number of subjects screened for the study will be provided. A summary of study disposition will be provided by study treatment showing the following:

- Number of subjects randomized
- Number of subjects treated
 - Number of treated subjects who completed the study
 - Number of treated subjects who discontinued early from the study
 - Primary reasons for early study discontinuation, with frequencies
 - Number of treated subjects who completed treatment
 - Number of treated subjects who discontinued treatment early
 - Primary reasons for early treatment discontinuation, with frequencies

The following additional disposition summary will be provided:

- Number of subjects who completed the Week 12 Visit
- Number of subjects who discontinued prior to the Week 12 Visit
 - Primary reasons for discontinuation prior to the Week 12 Visit, with frequencies

A listing of subject disposition will include analysis set flags (ITT, Safety, mITT, PP [Yes/No], Active Draining Fistula), dates of first and last dose of study drug, primary reason for subject discontinuation of study treatment, study completion status, primary reason for study termination, and date of last contact.

A listing of subject eligibility (inclusion or exclusion criteria exceptions) and a listing of subjects randomized but not treated will be provided.

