3.7.1.1. Treatment Compliance

Study drug compliance will be calculated as:

$$\frac{100 \times 0.5 \times (\text{number of capsules dispensed} - \text{number of capsules returned})}{(\text{date of last dose} - \text{date of first dose} + 1)}$$

Study drug compliance over the interval from first to last dose in the induction period and the study overall will be summarized as a continuous variable and by rounding to the nearest 0.1% and showing counts and percentages for the following disjoint categories:

- $\geq 120\%$;
- 110% to 120%;
- 90% to 110%;
- 80% to 90%;
- $< 80\%$;

Study drug administration information (date/time and study day) will be provided in a data listing. Study drug accountability information and study drug exposure and compliance will also be provided in data listings.

Study drug discontinuations and reasons for study drug discontinuation will be listed.

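### SAP 3.7.1 ends treatment duration at the drug-return date instead of the last dose for subjects who stop before Week 12 and in the overall-study formula, which misstates exposure whenever the two dates differ

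*SAP*

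**What the plan says.** SAP 3.7.1 (Extent of Exposure) defines Induction duration in weeks as the last Induction dose date minus the first dose date, plus one day, divided by seven. A note then says what the last Induction dose date means. It is "considered to be the Week 12 visit dose administration date for those that reach the Week 12 visit", and it is "equal to date of last study drug return for those who discontinue prior to Week 12 visit". The formula for the whole study puts the last return date in the numerator for everyone.

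The same section adds that "Calculated values will be rounded to 1 significant digit in the analysis datasets".

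Elsewhere the SAP works from the last dose:

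- The disposition listing in SAP 3.2.1 carries the "dates of first and last dose of study drug".
- Footnote J to the schedule in SAP 1.4 states that "Study drug dosing details will be entered from Day 1 (Induction) through ATE Week 48", or up to the last dose for a subject who stops early.
- SAP 3.7.1.1 summarises "Study drug compliance over the interval from first to last dose in the induction period and the study overall".
- The study periods in SAP 3.1.5 close at the last dose plus 5 days, and the adverse event windows in SAP 3.7.2 at the last dose plus 28 days. The Induction versions of both close at the ATE Day 1 dose if that comes sooner.

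On timing, Protocol 6.3.15 says of the Early Study Drug Discontinuation visit: "This visit will be conducted within 5 days after the last dose of study drug, if possible". Drug accountability is on that visit's procedure list.

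**The concern.** A return date records drug accountability, not dosing. Using it as the end of treatment counts days on which no drug was taken when the return follows the last dose, and loses treated days when the final supply does not come back. It also means that, in one Induction table, subjects who reach Week 12 are measured to a dose and those who stop earlier are measured to a return.

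Safety is a primary objective and extent of exposure is one of its summaries. SAP section 1 records that the study was terminated early and that the exploratory ATE efficacy analyses are dropped. More subjects may therefore stop before ATE Week 48, and those are the subjects for whom the overall-study rule can go wrong.

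**Working it through.** **The plan's own figure.** SAP 1.2.2 gives a maximum of 60 weeks of treatment. On nominal days, Week 12 is Day 84, ATE Day 1 is Day 84 + g with g from 1 to 7, and ATE Week 48 is ATE Day 336. The last dose is then on Day 84 + g + 335 = 419 + g. With g = 1, 420/7 = 60.0 weeks, which agrees. With g = 7, 426/7 = 60.9 weeks.

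**Who is affected.**

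- *Induction, reached Week 12:* the end date is a dose date. Error 0.
- *Induction, stopped earlier:* error = (return date − last dose date)/7.
- *Overall, completed ATE Week 48:* Protocol 6.3.13 lists the last dose and drug accountability at the same visit. Error 0 if drug is returned there.
- *Overall, stopped earlier:* the same error formula.

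**Return after the last dose.** With the full 5-day lag, the error is 5/7 = 0.71 week.

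| Last dose | To last dose (weeks) | To return (weeks) | Excess |
|---|---|---|---|
| Day 14 | 14/7 = 2.00 | 19/7 = 2.71 | 5/14 = 35.7% |
| Day 28 | 28/7 = 4.00 | 33/7 = 4.71 | 5/28 = 17.9% |
| Day 56 | 56/7 = 8.00 | 61/7 = 8.71 | 5/56 = 8.9% |

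The mismatch would show in the outputs. Protocol 5.2 has two tablets once daily, so a fully compliant subject with a last dose on Day 14 has taken 28. SAP 3.7.1.1 gives 100 × 0.5 × 28/14 = 100% compliance over 14 days, while SAP 3.7.1 gives 19 days of exposure.

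**Late return (assumption).** If drug came back only at the End of Study visit, 28 days after the last dose, the error would be 28/7 = 4.0 weeks. For a last dose on Day 14 that is 42/7 = 6.0 weeks against 2.0.

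**No return of the last supply.** Suppose the last recorded return is at the Week 4 visit (Day 28) and the subject doses until the day before Week 8 (Day 55), then is lost. The error is (28 − 55)/7 = −27/7 = −3.9 weeks. After a Week 8 dispensing it is (56 − 83)/7, the same. SAP 3.7.1 has no rule for a missing final return.

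**Effect on an arm mean.** The shift is the share of early discontinuers × lag/7. The documents give no share. For an assumed 5% to 30%:

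- 5-day lag: 0.05 × 5/7 = 0.04 to 0.30 × 5/7 = 0.21 week.
- 28-day lag: 0.05 × 4 = 0.2 to 0.30 × 4 = 1.2 weeks.

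**The case against.** The strongest reply is that little depends on this. Exposure is a descriptive summary, adverse events are reported as numbers and percentages of subjects, and no visible section uses duration as a denominator. The number of doses, summarised beside duration, does not depend on the return date. First and last dose dates are listed by subject, so a reader could recover the right duration. All of this stands, and it keeps the point minor. It does not explain why an available last dose date is set aside.

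Four stronger readings are tempting, and the documents do not support them:

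- *Every overall-study figure is inflated.* The formula covers everyone, but ATE Week 48 completers dose and have drug accountability at one visit, so their error is zero if they return drug there.
- *Exposure could be tripled, as in the Day 14 example with return at End of Study.* Protocol 6.3.14 lists no drug accountability at that visit. The general instruction in Protocol 5.4 to bring drug back at each visit makes a late return possible, not planned.
- *One arm is favoured.* That needs different discontinuation or return patterns by arm, and the documents give none.
- *The rounding rule would store 12.1 weeks as 10.* This is the literal meaning of one significant digit. SAP 3.7.1.1 rounds to 0.1% and SAP 5.3.1.6 to one decimal place, so decimal places were almost certainly meant.

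It can also be said that a last-dose rule still counts the interval between Week 12 and ATE Day 1 in the overall duration. This is true: it is the difference between 60.0 and 60.9 weeks above. It is a separate matter, present under either rule.

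**Conclusion.** The point holds in a limited form. For early discontinuers, in Induction and overall, SAP 3.7.1 as written gives a duration that differs from first-to-last-dose time whenever the return and the last dose fall on different days. The overstatement is at most 0.71 week per subject if the discontinuation visit takes place within 5 days of the last dose and drug is returned there. It is about 4 weeks if, as an assumption, drug comes back only at End of Study. The error can also be an understatement, by up to about 27 days, if supply dispensed at Week 4 or Week 8 is never returned. The direction is therefore not fixed, and the size of any shift in an arm's mean depends on discontinuation shares that the documents do not give. No efficacy result is touched. It is worth correcting but of low severity.

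**What to change.** In SAP 3.7.1, define both durations as (date of last dose − date of first dose + 1)/7, using the last Induction dose for the Induction figure and the last dose in the study for the overall figure. Use the return date only when the last dose date is missing, and flag those subjects in the exposure listing, since the return date can err in either direction. A table footnote could state that the overall duration includes the interval between Week 12 and ATE Day 1.

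As an editorial point, replace one significant digit with one decimal place in the rounding rule, and make the same correction to the presentation rules for the summary statistics.

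The cost is SAP wording and the matching derivation. No new data are needed.

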1.2. Study Design

1.2.1. Summary of Study Design

This study includes 3 phases: Screening, Induction, and Active Treatment Extension (ATE). Screening is up to 5 weeks long. The Induction phase of the study is a multi-center, randomized, double-blind, placebo-controlled, parallel-group study evaluating 2 dose levels of TD-1473 (80 mg or 200 mg; approximately 60 subjects per dose level) compared to placebo (approximately 40 subjects) for 12 weeks in subjects with moderately-to-severely active Crohn's Disease (CD).

Subjects who complete the Induction phase will continue to receive TD-1473 in ATE, either at 80 mg or 200 mg, for up to 48 additional weeks.

Figure 1: Study Design Schematic

Screening:

To determine eligibility, subjects will undergo assessments during the Screening period (up to 35 days prior to Day 1 dosing) as outlined in the Schedule of Study Procedures (Section 1.4). Disease activity will be assessed by the clinical scores, based on symptoms reported on a daily diary, which will be captured electronically beginning the day after Screening Stage 1.

Subjects who meet all inclusion (with the exception of the endoscopic subscore criterion) and no exclusion criteria, will undergo ileocolonoscopy with biopsies to complete Screening Stage 2. The aim of this endoscopic exam is to assess the SES-CD score by central reading and to obtain biopsies.

Induction

If the subject meets all eligibility criteria, the subject may be randomized into one of the following 3 treatment groups in a 3:3:2 ratio: TD-1473 80 mg, TD-1473 200 mg, or placebo.

The randomization will be stratified by prior biologics failure and CDAI score category (≤ 300 , > 300) at the Screening Stage 2 visit (using laboratory data from Screening Stage 1 for the score calculation). Approximately 40-60% of subjects randomized will have failed prior treatment with biologics. Subjects will be treated for 12 weeks and assessed for the various endpoints, including those that incorporate findings from an ileocolonoscopy and biopsies at the Week 12 visit. Corticosteroids will start to be tapered at Week 8. Subjects will undergo clinic study visits every 4 weeks in accordance with the Schedule of Assessments

(Section 1.4). During this time, subjects will continue to fill out a daily diary.

ATE:

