3.1.3. Visit Windows

All assessments will be summarized using analysis windows.

The terminology of unscheduled will be applied to assessments that are outside an analysis window regardless of the nominal label associated with the assessments in the EDC system.

The following visit windows will be used in the summary of clinical data.

Table 6: Visit Analysis Windows

Nominal Visit	Nominal Day	Start (days)	Stop (days)
Screening	NA	-28	-1
Baseline	1	1	Induction Day 1
Week 4	Induction Day 28	Induction Day 21	Induction Day 35
Week 8	Induction Day 56	Induction Day 49	Induction Day 63
Week 12	Induction Day 84	Induction Day 77	Earliest of: 
 • ATE Day 1 dose date • Induction Day 98 (Induction Day 112 for SES-CD score)
ATE Week 4	ATE Day 28	ATE Day 21	ATE Day 35
ATE Week 8	ATE Day 56	ATE Day 49	ATE Day 63
ATE Week 16	ATE Day 112	ATE Day 105	ATE Day 126
ATE Week 24	ATE Day 168	ATE Day 161	ATE Day 182
ATE Week 36	ATE Day 252	ATE Day 245	ATE Day 266
ATE Week 48	ATE Day 336	ATE Day 329	ATE Day 350

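### SAP 3.7.1 rounds treatment duration to one significant digit, so a full 12-week Induction is stored and reported as 10 weeks

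*SAP*

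**What the plan says.** SAP 3.7.1 sets the unit for the Induction period: "Duration of treatment will be displayed in weeks and calculated for the induction period as" the last Induction dose date minus the first dose date, plus one, divided by 7. For completers the end date is fixed: "Last induction phase dose date is considered to be the Week 12 visit dose administration date for those that reach the Week 12 visit". Subjects who stop earlier take the date of last study drug return instead. A second formula of the same form covers the whole study.

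Two layers of rounding follow. The first is on the data: "Calculated values will be rounded to 1 significant digit in the analysis datasets". The second is on the statistics: "Mean, median, Q1, Q3: 1 significant digit", "Standard deviation: 2 significant digits" and "Minimum, maximum: 1 significant digit".

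Nothing in the section gives the term significant digit a special meaning. Elsewhere the SAP uses decimal wording when it means decimals. Section 5.3.1.6 keeps time since diagnosis unrounded for statistics and shows it to one decimal place, and section 3.7.1.1 rounds compliance to the nearest 0.1%.

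**The concern.** Induction is planned at 12 weeks and the whole treatment course at up to 60. At one significant digit, any value of 10 or more is rounded to the nearest ten. For a duration in weeks, that removes most of the information the variable is meant to carry.

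Because the rule acts on the analysis dataset and not only on the display, the precision is lost before any statistic is calculated. A programmer must either implement the sentence and print a 10-week Induction, or depart from the SAP without saying so. A validator working from the SAP could not confirm the second choice. Safety and tolerability is a primary objective (SAP 1.1.1), and duration of treatment is a named safety output (SAP 3.7), so the table will be read.

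**Working it through.** **Inputs**
- Formula: (last dose date − first dose date + 1)/7, in weeks (SAP 3.7.1).
- Planned Induction: 12 weeks. SAP 1.2.1 states "Subjects will be treated for 12 weeks and assessed for the various endpoints".
- Nominal Week 12: "Induction Day 84", with an analysis window from Day 77 to Day 98 at the latest (SAP 3.1.3).
- Rounding: one significant digit, ties rounded up (the tie rule is my assumption).

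**Reproducing the planned length.** With the first dose on Day 1 and the last on Day 84: (84 − 1 + 1)/7 = 12.0 weeks. The formula is correct and returns the planned 12 weeks.

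**Applying the rounding rule to Induction**

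| End day | Weeks | 1 significant digit | 1 decimal place |
|---|---|---|---|
| 66 | 9.43 | 9 | 9.4 |
| 67 | 9.57 | 10 | 9.6 |
| 70 | 10.00 | 10 | 10.0 |
| 77 | 11.00 | 10 | 11.0 |
| 84 | 12.00 | 10 | 12.0 |
| 87 | 12.43 | 10 | 12.4 |
| 98 | 14.00 | 10 | 14.0 |
| 104 | 14.86 | 10 | 14.9 |
| 105 | 15.00 | 20 | 15.0 |

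- At Day 84 the understatement is (12 − 10)/12 = 16.7%. Across the Week 12 window it runs from (11 − 10)/11 = 9.1% at Day 77 to (14 − 10)/14 = 28.6% at Day 98.
- All days from 67 to 104 are stored as 10, and the Week 12 window lies wholly inside that range.
- A subject whose end day is 70 is stored identically to a completer.
- If more than half of an arm has its end day in that range, the stored median is 10 whatever the true median. If the whole arm does, the SD is 0.

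**Whole study**
- Day 384 is 54.86 weeks and is stored as 50, an error of 4.86 weeks.
- Days 385 to 454 (55.0 to 64.86 weeks) are all stored as 60. The error at Day 454 is again 4.86 weeks; at the exact tie of 55.0 it is 5.0.

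**Effect on a printed mean.** Individual values are rounded first, then averaged, then rounded again.
- 90% at 12 weeks and 10% at 2 weeks: true mean 0.9 × 12 + 0.1 × 2 = 11.0; stored mean 0.9 × 10 + 0.1 × 2 = 9.2; printed 9.
- 60 subjects at 12.0 weeks: true mean 12.0; printed 10.
- 54 at 12.0 and 6 at 10.0: true mean (54 × 12 + 6 × 10)/60 = 11.8; printed 10.

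**The case against.** The strongest reply is that this is a slip of terminology. A pattern of one for location and range and two for the SD is the usual decimal-place convention, nearby rules use decimals, and a programmer may well read it that way. That is probably what was meant. However, the sentence is a working rule for building a dataset, no other passage overrides it, and the SAP uses the term decimal place correctly elsewhere.

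A second reply is that early stopping remains visible. SAP 3.2.1 counts subjects who completed or stopped before Week 12 and lists first and last dose dates. SAP 3.7.1 also summarises number of doses, although it does not say whether the same presentation rule applies to them. Durations can therefore be recomputed from the listings. This stands, and it limits the damage.

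Three stronger readings are tempting, and the documents do not support them:
- A reader might infer that the error spreads to every safety table. Adverse event tables use numbers and percentages of subjects (SAP 3.7.2), and laboratory, vital sign and ECG data are summarised by visit or category. Compliance is computed from capsule counts and dates (SAP 3.7.1.1), not from the rounded duration.
- A reader might infer biased exposure-adjusted event rates. None is planned in the visible text.
- A reader might infer that any arm with a true mean between about 9.5 and 12.6 weeks prints as 10. The first layer of rounding prevents this, as the arm with true mean 11.0 and printed mean 9 shows. Arms with different stopping patterns can print the same mean, but they need not.

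**Conclusion.** Wrong as written, with a narrow effect. Taken literally, SAP 3.7.1 stores and reports a Day 84 completer as 10 weeks instead of 12.0 (16.7% low). It also gives every end day from 67 to 104 the same value and allows whole-study errors of almost 5 weeks. The stored variable then cannot separate completers from subjects who stopped from Day 67 on.

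The conclusion rests on the ordinary meaning of significant digit and on the SAP's own formula and nominal day. The 16.7% applies to Day 84 exactly; other days in the Week 12 window give other percentages. The consequences stop at the duration variable and the exposure summaries. Efficacy analyses and the power statement do not use duration. This is a minor correction, worth making because the rule is explicit and the result is plainly false.

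**What to change.** In SAP 3.7.1, replace significant digit(s) with decimal place(s) throughout: one for the mean, median, Q1, Q3, minimum and maximum, and two for the SD. With that change Days 77, 84, 87 and 98 read 11.0, 12.0, 12.4 and 14.0 weeks and stay distinct.

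Preferably also leave the dataset value unrounded and round only for display, following SAP 5.3.1.6. This second step is a matter of consistency: once the wording is corrected, rounding stored values to 0.1 week moves any value by at most 0.05 week (0.35 day).

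The cost is a small wording change in one section, with no effect on data collection or on any other planned analysis.
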